## 6.2. Handling of Missing Data

All statistical analyses on the functional endpoints will be performed using only those patients with available data required for endpoint analysis. No missing value imputation will be performed.

No imputation will be done if the date variables are completely missing. For partial dates, only adverse event (AE) onset date will be imputed as follows:

- 1) If both month and day are missing
  - a. If the AE onset year is the same year as index procedure then use index procedure date to impute this AE onset date
  - b. Otherwise, assign January 1st for this AE onset date
- 2) If only day is missing
  - a. If the AE onset year and month are the same as the procedure ones then use the index procedure date to impute the AE onset date
  - b. Otherwise, assign '01' as the day for the AE onset date

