18 CHRONIC MR SEVERITY GRADING BY ECHOCARDIOGRAPHY

This table is derived from the 2017 American Society of Echocardiography Native Valve Regurgitation Guidelines.

The only modification of note to the guidelines is the addition of a separate category for Trace MR. This category will be used to characterize regurgitation that is clinically insignificant and too little to quantify. In addition, the core lab overall has also subdivided the moderate MR category into mild-moderate and moderate-severe subcategories.

	Trace (0-1+)	Mild (1+)	Mild-Moderate (2+)	Moderate-Severe (3+)	Severe (4+)
Structural					
MV morphology	None or mild leaflet abnormality	None or mild leaflet abnormality	Moderate leaflet abnormality or moderate tenting	Moderate leaflet abnormality or moderate tenting	Severe valve lesions
LV and LA size	Usually normal	Usually normal	Normal or mild dilation	Normal or mild dilation	Dilated
Qualitative Doppler					
Color flow jet area	Small, central, narrow, brief	Small, central, narrow, brief	Variable	Variable	Large central jet (>50% of LA) or eccentric wall-impinging jet of variable size
Flow convergence	Not visible	Not visible, transient or small	Intermediate in size and duration	Intermediate in size and duration	Large throughout systole
CW Doppler jet	Faint	Faint/partial/parabolic	Dense but partial or parabolic	Dense but partial or parabolic	Holosystolic/dense/triangular
Semiquantitative					
Vena contracta width (cm)	< 0.3	< 0.3	Intermediate	Intermediate	≥ 0.7
Pulmonary vein flow	Systolic dominance	Systolic dominance	Normal or systolic blunting	Normal or systolic blunting	Minimal to no systolic flow / systolic flow reversal
Mitral inflow	A wave dominant	A wave dominant	Variable	Variable	E wave dominant (> 1.2 m/sec)
Quantitative					
EROA (cm ²)	< 0.2	< 0.2	0.20 – 0.29	0.30 – 0.39	≥ 0.40 (may be lower in secondary MR with elliptical EROA)
Regurg Vol (ml)	< 30	< 30	30 – 44	45 – 59	≥ 60 (may be lower in low flow conditions)
Regurg Fract (%)	< 30	< 30	30 – 39	40 – 49	≥ 50

Reference: Zoghbi et al. Recommendations for Noninvasive Evaluation of Native Valve Regurgitation. Journal of the American Society of Echocardiography. Volume 30, Number 4.

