#### 3.2. Secondary Endpoints and Clinical Outcomes

- Mitral regurgitation reduction at 30 days, 6 months, 1 year and annually thereafter over baseline
- All-cause mortality at 30 days, 6 months, 1 year, and annually thereafter
- Recurrent heart failure hospitalization at 30 days, 6 months, 1 year, and annually thereafter
- Re-intervention rates for mitral regurgitation at 30 days, 6 months, 1 year and annually thereafter
- Composite of major adverse events (MAE) defined as cardiovascular mortality, stroke, myocardial infarction, new need for renal replacement therapy, severe bleeding and re-intervention for study device related complications at 6 months, 1 year and annually thereafter
- Change in Left Ventricular End Diastolic Volume (LVEDV) at 6 months and 1 year and annually thereafter over baseline

- Change in Left Ventricular End Systolic Volume (LVESV) at 6 months and 1 year and annually thereafter over baseline
- Change in Pulmonary Artery Systolic Pressure at 6 months and 1 year and annually thereafter over baseline
- Change in 6MWT distance at 6 months and 1 year over baseline
- Change in Quality of Life (QoL) score, as measured by Kansas City Cardiomyopathy Questionnaire (KCCQ), and EQ5D at 30 days, 6 months and 1 year and annually thereafter over baseline
- Change in NYHA Functional Classification at 6 months and 1 year and annually thereafter over baseline
- Change in BNP/NT-pro-BNP level at 6 months and 1 year and annually thereafter over baseline
- Change in tricuspid regurgitation at 6 months and 1 year and annually thereafter over baseline
- Change in effective regurgitant orifice area (EROA) at 30 days, 6 months, 1 year and annually thereafter over baseline
- Change in mitral regurgitant volume at 30 days, 6 months and 1 year and yearly thereafter over baseline

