## 6. STATISTICAL ANALYSES

### 6.1. General Considerations

a. For continuous variables, summary statistics will include number of observations, mean, median, standard deviation, minimum, maximum, and 95% confidence intervals (based on normal distribution, unless otherwise specified) per table shells.

b. For categorical variables, summary statistics will include counts, percentages, and 95% Clopper-Pearson confidence intervals per table shells. In general, the denominator for the percentage calculation will be based on total number of subjects with evaluable data for a specified time point unless otherwise specified. Subjects with missing data will be excluded from the denominator.

c. Survival analysis techniques will be used to analyze the time-to-event variables. Summaries will include the number of subjects at risk, number of events, and number of subjects with the event. Subjects without events will be censored at their last known event-free time point. If this event-free time point occurs after the analysis time point, the days to event variable will be set equal to the analysis time point so that the subject will be included in the analysis. For subjects who did not have an event or early withdrawal and have not yet completed the analysis visit, they will be censored at their last information date. Time to first event curves will be constructed using Kaplan-Meier estimates and all post procedure results will be summarized with Kaplan-Meier estimates of event rates. Hazard ratios, confidence interval for the hazard ratios, and p-values may also be presented from a Cox proportional hazards model.

d. Descriptive statistics will be provided at each follow-up assessment, including change from baseline to subsequent time point for selected endpoints. Paired (i.e., subjects with available data at both baseline and respective time point) and unpaired data will be presented separately.

e. If insufficient data are available for summary statistics, then data will be provided only as listings.

f. Unless otherwise specified, descriptive analysis will be performed for all data. Nonparametric techniques may be used if the data does not meet the assumptions of parametric tests.

g. All analyses will be performed using SAS® Software version 9.4 or later (SAS Institute, Inc., Cary, NC).

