#### 6.4. Analyses of Secondary Endpoints

Mitral regurgitation reduction from baseline at 30 days, 6 months, 1 year and annually thereafter will be summarized with counts and percentages.

All-cause mortality rates at 30 days, 6 months, 1 year, and annually thereafter and corresponding 95% confidence intervals will be computed using the Kaplan-Meier algorithm with the standard errors being computed using Greenwood's formula.

Recurrent heart failure hospitalization at 30 days, 6 months, 1 year, and annually thereafter will be analyzed using Poisson regression.

Re-intervention rates for mitral regurgitation at 30 days, 6 months, 1 year and annually thereafter will be summarized with counts and percentages.

Composite of major adverse events (MAE) defined as cardiovascular mortality, stroke, myocardial infarction, new need for renal replacement therapy, severe bleeding and re-intervention for study device related complications at 6 months, 1 year and annually thereafter will be summarized with counts and percentages.

Change from baseline in Left Ventricular End Diastolic Volume (LVEDV), Left Ventricular End Systolic Volume (LVESV), Pulmonary Artery Systolic Pressure, 6MWT distance, BNP/NT-pro-BNP level, effective regurgitant orifice area (EROA) and mitral regurgitant volume at the protocol specified timepoints in the secondary endpoints and clinical outcomes section will be summarized by mean and standard deviation for the PP population. For the analyses of six minute walk test (6MWT), subjects unable to perform the walk due to a medical reason will be considered to have walked an actual distance of zero.

Change from baseline in Quality of Life (QoL) score, as measured by Kansas City Cardiomyopathy Questionnaire (KCCQ), and EQ5D at 30 days, 6 months and 1 year and annually thereafter will be

summarized by mean and standard deviation. Patients that are missing a baseline or follow up values will be excluded from the analysis.

Change from baseline in NYHA Functional Classification at 6 months, 1 year and annually thereafter will be presented as shift from baseline for each of the pre-specified follow-up periods. Subjects that are missing a baseline or follow-up values will be excluded from the paired analysis.

Change from baseline in tricuspid regurgitation at 6 months, 1 year and annually thereafter will be summarized with counts and percentages.

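### The plan gives patients reduced to trace MR no value for EROA or regurgitant volume, so unless the core lab records one they leave the mean change because they did well

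*SAP*

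**What the plan says.** Two secondary endpoints are quantitative echo measures followed to 5 years. SAP 3.2 lists "Change in effective regurgitant orifice area (EROA) at 30 days, 6 months, 1 year and annually thereafter over baseline", and mitral regurgitant volume on the same schedule. SAP 6.4 names "effective regurgitant orifice area (EROA) and mitral regurgitant volume at the protocol specified timepoints" among the changes from baseline that "will be summarized by mean and standard deviation for the PP population".

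Protocol Section 18 adds a trace category to the published MR grading and says of it: "This category will be used to characterize regurgitation that is clinically insignificant and too little to quantify". The Section 18 table gives trace the same quantitative entries as mild: EROA below 0.2 cm2 and regurgitant volume below 30 ml. These are limits, not values.

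On missing values, SAP 6.2 says "All statistical analyses on the functional endpoints will be performed using only those patients with available data required for endpoint analysis", followed by "No missing value imputation will be performed". SAP 6.1(d) adds: "Paired (i.e., subjects with available data at both baseline and respective time point) and unpaired data will be presented separately".

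For a different outcome, the six-minute walk, SAP 6.4 does settle what an unmeasurable result means: "subjects unable to perform the walk due to a medical reason will be considered to have walked an actual distance of zero". There is no counterpart for EROA or regurgitant volume.

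**The concern.** Entry requires 3+ to 4+ MR (Protocol 7.7.1), so the trace grade can arise only after treatment, and it marks the largest reductions. If such a patient has no number for EROA or regurgitant volume, no change can be computed and nothing is substituted. The value is then absent because of the outcome, which is the case in which an available-case mean misleads.

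Three things would follow. The mean change would not respond to the best results, since it is the same whatever share of patients reaches trace. The standard deviation and confidence interval would describe the same reduced set. And the patients contributing would change from visit to visit as MR grades move, so part of a 5-year trend could be patients entering or leaving the quantifiable group. This matters for a study whose stated objectives include guiding future study designs (Protocol 7.2, SAP 2.1).

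**Working it through.** The plan states no expected value for either endpoint, so there is no figure to reproduce. The size of the effect can only be illustrated.

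**Inputs.** From the documents: trace limits of 0.2 cm2 and 30 ml, severe cut-points of 0.40 cm2 and 60 ml (Protocol Section 18), and an analysis population of 60. Assumed: baseline mean b, the same in trace and other patients; follow-up mean r in patients with a measured value; share p graded trace and unmeasured; true mean t in those trace patients. I place b and r at or near the Section 18 cut-points.

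**Formulas.**
- Planned (available-case) mean change = r − b
- All-patient mean change = (1 − p)r + pt − b
- Understatement of the reduction = p(r − t)

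**EROA with b = 0.40, r = 0.20 cm2, t = 0:**

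| p | Patients in the mean, of 60 | Planned change | All-patient change | Gap | Planned ÷ all-patient |
|---|---|---|---|---|---|
| 10% | 54 | −0.20 | −0.22 | 0.02 | 91% |
| 20% | 48 | −0.20 | −0.24 | 0.04 | 83% |
| 30% | 42 | −0.20 | −0.26 | 0.06 | 77% |
| 50% | 30 | −0.20 | −0.30 | 0.10 | 67% |

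**Regurgitant volume with b = 60, r = 30 ml, t = 0:** planned −30 ml throughout, against −33, −36, −39 and −45 ml at the same shares. The gap is 3 to 15 ml.

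**Smaller effects.** With b = 0.38, r = 0.18 and t = 0.05 cm2:
- p = 5%: gap 0.05 × 0.13 = 0.0065; 0.0065/0.2065 = 3%
- p = 10%: gap 0.013; 0.013/0.213 = 6%
- p = 20%: gap 0.026; 0.026/0.226 = 12%

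If t equals r, the gap is zero. If r is only 0.10 cm2 and t = 0, the gap is 0.01 to 0.05 cm2 for p = 10% to 50%.

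**Larger effects.** With b = 0.38, r = 0.18, t = 0 and p = 50%, the gap is 0.09 and 0.09/0.29 = 31%. The absolute gap does not depend on b, but the percentage does: with b = 0.30 and r = 0.20, a gap of 0.10 is half of an all-patient reduction of 0.20.

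**Spread.** Assume baseline SD 0.12, follow-up SD 0.07 in measured patients, independence and p = 30%. The planned SD is √(0.12² + 0.07²) = 0.14. With trace set to 0, the follow-up variance is 0.7 × 0.07² + 0.7 × 0.3 × 0.20² = 0.0118, and the SD of change is √(0.0144 + 0.0118) = 0.16.

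**Trend.** Take b = 0.40, p = 30%, r = 0.20 and t = 0 at one visit: planned change −0.20, all-patient change −0.26. Suppose the trace patients later worsen to a measurable 0.10 cm2 and the rest stay the same. The mean is now 0.7 × 0.20 + 0.3 × 0.10 = 0.17, and both changes are −0.23. The planned figure appears to improve from −0.20 to −0.23 while the patients as a whole went from −0.26 to −0.23.

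**Unpaired summary.** This does not repair the problem. Its baseline mean includes patients who later become trace, and its follow-up mean omits them.

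**The case against.** The strongest reply is that the loss of these patients is inferred. No section shows how the core lab records trace cases. The trace column prints quantitative limits, so the lab could enter 0, a small number or nothing. The rule could sit in the core lab's written guidelines (Protocol 10.2), the acquisition protocol in Appendix B or the SAP table shells (SAP 10), none of which is available here. If the lab enters a number, nothing is missing and this bias does not arise. That stands, and it makes the point conditional. It does not remove the gap in the SAP, because handling that determines an endpoint's mean should be stated there.

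Other replies have partial force:
- The available-case sentence in SAP 6.2 refers to functional endpoints, an undefined term that may not cover echo measures. But no other rule covers them, and a change still needs two numbers.
- SAP 6.1(a) already lists the number of observations and the median, so a shrinking denominator would be visible. It would not be explained: too small to quantify and no readable echo look alike.
- Trace patients still count in the graded MR-reduction endpoint, and the primary endpoints use MR grade, so those are unaffected.
- Understating the reduction cannot inflate a claim of benefit at a single visit. Trends are different, as the example shows.
- Zero is the most favourable value for the device, and the walk-test parallel is only partial, since zero there is a penalty. This is why zero needs a second, unfavourable analysis beside it.

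**Conclusion.** The concern holds conditionally. As written, the plan has no value for trace MR in the EROA and regurgitant volume analyses. Unless the core lab supplies one, patients leave the mean change because they did well, and the set of contributing patients shifts between visits. The understatement is p(r − t). With equal baseline means, b about 0.38 to 0.40 cm2, r about 0.18 to 0.20 cm2 and p up to 50%, it runs from near 0 to about one third of the true reduction. The documents give none of these quantities, so the actual size is unknown.

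A reader might infer more than this, without support:
- That the best responders certainly drop out. The core lab's recording rule is not in the documents at hand.
- That only patients with substantial residual MR remain. Mild (1+) patients with a measured value stay in.
- That SAP 6.1(d) confines the analysis to pairs. It has paired and unpaired data presented separately.
- That visits cannot be compared at all. The number of observations and the MR grades are planned summaries, which allow a cautious reading.

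The affected endpoints are secondary and descriptive, with no test or margin on them. This is a worthwhile SAP correction that leaves the primary endpoints and sample size untouched.

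**What to change.** Add a rule to SAP 6.4. When the core lab grades MR as none or trace and EROA or regurgitant volume is not quantifiable, keep the patient in the change-from-baseline analysis with the value set to 0. Repeat the analysis with the value set to the Section 18 upper limit, 0.2 cm2 or 30 ml. These limits are fixed across visits, and the two analyses bracket the mean for the patients concerned. For example, with b = 0.40, r = 0.20 and p = 30%, the bracket is −0.26 to −0.20 cm2. The lowest value quantified at a visit would be a poorer second choice, since it moves between visits and need not bound the result.

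Report quartiles beside the median that SAP 6.1(a) already lists. At each visit, count patients too small to quantify separately from those whose echo was absent or unreadable.

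The cost is a few lines of SAP text and one core-lab reason code, with no new visits or imaging. The drawback is a fixed value for a subgroup, which the second analysis bounds. If the core lab already records a number, the SAP need only say which.

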### 2.2. Study Design

This is a multi-center (up to 20 sites), multi-national, prospective, single arm study. The analysis population will consist of 60 patients. No site will be allowed to enroll more than 20% of the analysis population. All enrolled study patients will be assessed for clinical follow-up at the following intervals: 30 days, 6 months, 1 year and annually for 5 years post implant procedure. In addition, the study allows for 0 to 3 roll-in patients per site where allowed, for a total maximum of 60 roll-in patients. The overall study therefore allows for up to 120 patients: 60 in the analysis population, and up to 60 additional roll-in patients.

Of the total enrollment, 45 patients will be enrolled in the U.S. at up to 9 clinical sites. In the event that the 60-patient analysis cohort fills prior to the completion of the US EFS cohort, the US EFS cohort may continue to enroll until completed.

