## 6.3. Analyses of Primary Endpoints

### Safety:

The primary safety endpoint for this clinical study is a composite of major adverse events (MAE) defined as cardiovascular mortality, stroke, myocardial infarction, new need for renal replacement therapy, severe bleeding and re-intervention for study device related complications at 30 days. The safety endpoints on composite of major adverse events shall be analyzed via the Kaplan-Meier method.

In addition to the safety endpoint analysis, a summary of the percentage of patients who experience an early adverse event ( $\leq 30$  day post-procedure) will be reported for all adverse events. Additionally, linearized rates will be used to summarize adverse events for the late ( $> 30$  days) post-procedure period. The linearized rates will be reported as the number of events occurring after the early post-procedure period per year of patient survival.

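### SAP 6.2 imputes partial AE onset dates with no bound other than the procedure date, so some events after day 30 can be counted in the 30-day MAE endpoint

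*SAP*

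**What the plan says.** SAP 6.2 imputes one kind of date only, a partial AE onset date. It has four rules.

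- Month and day missing, procedure year: "If the AE onset year is the same year as index procedure then use index procedure date to impute this AE onset date".
- Month and day missing, any other year: "Otherwise, assign January 1 st for this AE onset date".
- Day missing, procedure month: "If the AE onset year and month are the same as the procedure ones then use the index procedure date".
- Day missing, any other month: "Otherwise, assign '01' as the day for the AE onset date".

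A wholly missing date is left alone: "No imputation will be done if the date variables are completely missing". The section does not mention the site's awareness date, the AE end date, the last event-free contact or death. It gives no sensitivity analysis for imputed dates.

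SAP 6.3 then relies on the onset date. For the primary safety endpoint, "The safety endpoints on composite of major adverse events shall be analyzed via the Kaplan-Meier method", at 30 days. All AEs are split at day 30: a percentage of patients for the early period, while "linearized rates will be used to summarize adverse events for the late" period. Clinical success (SAP 3.1) requires no MAE at 30 days. Follow-up is at "30 days, 6 months, 1 year and annually for 5 years post implant procedure" (SAP 2.2).

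**The concern.** The day-30 cut decides whether an event belongs to the primary safety endpoint and early AE table or to the late rate. For a partial date, SAP 6.2 decides the side mechanically. Suppose a patient has a clean 30-day visit, and at the 6-month visit reports an event for which only the year is known. If that year is the procedure year, the event is dated to day 0, although the trial's own records show that it happened after day 30.

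At stake are the 30-day MAE rate, clinical success, the late linearized rates and the event times in the Kaplan-Meier curves. The study is small, so a single event shows in the primary rate.

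**Working it through.** The documents give no figure to reproduce. The check applies the four rules to every combination of procedure date and true onset day.

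**Inputs.** The rules are from SAP 6.2. Early means day 30 or before and late means after day 30 (SAP 6.3). The analysis population is 60 and the first analysis is at 30 patients (SAP 2.2 and 4).

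**Assumptions, not in the documents.** Procedure dates are uniform over a 365-day year, and onset is uniform over days 0 to H. H is 180, 365, 730 or 1825 days. All shares are conditional on the date being partial.

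**Denominator.** Late combinations = 365 × (H − 30): 54,750, 122,275, 255,500 and 655,175.

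**Month and day missing.**

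- Every late event in the procedure year goes to day 0. Over a full year the count is 1 + 2 + … + 334 = 334 × 335 / 2 = 55,945. For H = 180 it is (1 + … + 150) + 184 × 150 = 11,325 + 27,600 = 38,925.
- A next-year event goes to 1 January. That is within 30 days only for the 30 procedure dates from 2 to 31 December. The counts are 30 × 150 = 4,500 (H = 180), 30 × 335 = 10,050 (H = 365) and 30 × (364 + 335) / 2 = 10,485 (H = 730 and 1825).

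**Only the day missing.**

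- The procedure-month rule cannot move a late event, because no day in the procedure month is later than day 30.
- The 1st-of-month rule moves an event only if that 1st falls by day 30, so true onset can be no later than day 60. Enumeration gives 5,373 late combinations moved in, at every H shown.

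| H (days) | Month unknown | Day unknown |
|---|---|---|
| 180 | 43,425 / 54,750 = 79% | 5,373 / 54,750 = 9.8% |
| 365 | 65,995 / 122,275 = 54% | 5,373 / 122,275 = 4.4% |
| 730 | 66,430 / 255,500 = 26% | 5,373 / 255,500 = 2.1% |
| 1825 | 66,430 / 655,175 = 10% | 5,373 / 655,175 = 0.8% |

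No early event was moved out of the window in any run.

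**Examples.**

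| Procedure | True onset | Unknown | Imputed | Moved in? |
|---|---|---|---|---|
| 1 Feb | 15 Oct, day 256 | month | day 0 | yes |
| 15 Dec | next 1 Sep, day 260 | month | 1 Jan, day 17 | yes |
| 15 Nov | next 1 Sep, day 290 | month | 1 Jan, day 47 | no |
| 20 Jan | 26 Feb, day 37 | day | 1 Feb, day 12 | yes |
| 10 Jan | 20 Jun, day 161 | day | 1 Jun, day 142 | no |

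**Effect of one moved patient.** This takes complete follow-up to day 30 and no other early MAE in that patient. 1/60 = 1.7 points; 1/30 = 3.3 points. For illustration, 3/60 = 5.0% (exact 95% CI 1.0 to 13.9) becomes 4/60 = 6.7% (1.8 to 16.2).

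**The case against.** **It will hardly ever touch an MAE.** This largely stands. Protocol 8.1 makes the event date part of the minimum information at first notification, sets short reporting times and requires source documents for adjudicated events. MAE components such as stroke, dialysis or re-intervention normally leave dated records, and the CEC adjudicates. The documents give no count of partial dates. Exposure is greater in the early and late tables, which cover all AEs. However, the SAP does not say that an adjudicated date replaces an imputed one.

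**The planned 30-day analyses have little to misdate.** This stands in part. When the last patients reach day 30, only earlier enrollees have late follow-up. Later data cuts are more exposed.

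**The bias is cautious.** This is true of the 30-day MAE rate, in a descriptive single-arm study with no test of that rate. It is not true of the late linearized rate, which loses the same events for a permanent implant followed for 5 years.

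**Stronger readings.** A reader might infer that the rules ignore all timing information, or that late events with partial dates are moved in as a matter of course. The text does not support either. The procedure date serves as a lower bound in two of the four rules, most next-year events with month unknown stay late, and so do most late events with only the day unknown. Nor can 54% be read as a property of this trial: it depends on a 1-year horizon and on the date being partial.

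**Conclusion.** The point holds as a defect in a stated rule, not as a forecast of material bias in the primary result. The rules can assign a date that contradicts the trial's own visit records. With month unknown this happens to every late event in the procedure year; a next-year event reaches the window only after a December procedure. With only the day unknown it is confined to true onsets up to about day 60.

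The conditional shares rest on assumed uniform procedure dates and event times, and fall steeply with a longer horizon. The direction does not depend on those assumptions: 30-day MAE can only be overstated, while clinical success and the late rate can only be understated. Few MAEs are likely to be involved. The change is still worth making, because one event is visible at this sample size and the correction is cheap.

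**What to change.** Amend SAP 6.2 so that a partial onset date becomes the earliest date that

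- agrees with the known year or month;
- is no earlier than the procedure date (for post-procedure events, since Protocol 8.1 captures AEs from enrollment) and no earlier than the last contact at which the event was documented absent, where that is recorded; and
- is no later than the site's awareness date, death, or the AE end date if collected.

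This keeps the cautious choice of the earliest date but confines it to what is possible. List every MAE with an imputed date. Report 30-day MAE twice, with events whose feasible interval spans day 30 counted in and counted out.

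The cost is a paragraph in the SAP, slightly more programming and a small sensitivity table. Protocol 8.1 already requires the awareness date. The case report forms are not among the documents, so whether end dates and event-free contacts are recorded has to be checked; the rule works with whichever bounds exist.
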